## **STUDY PROCEDURES**

Data collection includes patient descriptive data as well as three groups of outcomes: geriatric syndromes, medications and health status, safety and healthcare utilization. Table 1 shows a summary of the study timepoints along with the corresponding assessments. Upon enrollment, hospitalized participants complete interviewer-administered questionnaires, which require approximately 45 minutes per participant. Following

discharge to SNF, facility staff is required to assess all residents upon SNF admission and discharge using the standardized Minimum Data Set (MDS), which includes an assessment of these same geriatric syndromes using similar scales. The baseline hospital questionnaires are repeated by research staff via telephone 7-10 days after PAC discharge and in-person in the participant’s place of residence at 90-days after PAC discharge. *(During the COVID-19 pandemic, the VUMC IRB allowed the 90-day visits to be completed as telephone calls or using Vanderbilt’s HIPAA compliant video technology to limit exposure risks to both participants and staff).* A telephone interview is also conducted at 60-days post SNF discharge to assess medications and health-related measures. If a participant has a follow-up outpatient visit scheduled at VUMC during any of these time frames, an effort is made to conduct the interview in-person during that visit, if they prefer. For assessments completed in-person, the study team provided hearing and visual aids if necessary (e.g., hearing amplifiers and large font printed response cards with Likert scale categories). Both the intervention and control groups will be monitored using the same data collection schedule and measures. All interview assessments are completed by trained research personnel on our multidisciplinary team which includes a social worker, geriatric nurse practitioners, clinical pharmacists, geriatrician, hospitalist, and psychologist.

In the event a participant is unable to complete assessments due to delirium or cognitive impairment, their designated surrogate or caregiver (e.g., child, spouse, assisted living facility nurse) is interviewed to complete assessments which are validated for use with surrogates. Assessments that can be completed by surrogates include the ICIQ (urinary incontinence), Determine, falls, pressure ulcers, medication history, and demographics.

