### **Primary Outcomes - Medications**

Total number of Medications: Data sources include the participant's VUMC 'pre-hospital medication list', patient/family interview, pharmacy refill records, Controlled Substance Monitoring Database (CSMD), and outside hospital/PAC medical records. We include both prescription and over-the-counter medications (OTC) (vitamins, herbal supplements also included) administered by the following routes: oral, intravenous, intramuscular and ophthalmologic medications. All participants and/or their surrogates receive a baseline structured interview and chart review to determine any medication that has the potential to be continued at the time of hospital discharge to including pre-hospital medications and active in-hospital medications not on the pre-hospital medication list. Pre-hospital medications are confirmed by patient/ family interview and pharmacy refill records (including mail-order pharmacies) for the three months prior to hospitalization. Patient/surrogate are given specific prompts if they report no OTC usage, for example, asking them if they take anything for sleep disturbances, constipation, or allergies. If a patient is admitted from SNF or an outside hospital, we will request a copy of the MAR for the past 30 days. Current medications are defined as those taken within 30 days prior to hospitalization. At PAC discharge, the discharge medication list serves as the outcome data source. During follow-up calls at 7 and 60 days, study team asks the patient or surrogate for the status of each medication on the enrollment medication list to determine if and how they are taking it. Then the study team prompts for any new medications the patient may be using. In preparation for the 90-day visit, the study team completes a pharmacy record review similar to enrollment. At the 90-day visit, the study PharmD or NP reviews all the medication bottles in the home and asks the patients if and how they are using each.

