## Incorporate Patient Preferences

Following medication targeting (Figure 3. 2a) intervention participants or their surrogates receive a structured interview by the intervention pharmacist (PharmD) or nurse practitioner (NP) to elicit their preferences regarding medications identified for deprescribing. Surrogates are included in the conversation if the patient's cognitive deficits preclude their ability to fully participate, if the patient prefers to have the surrogate involved in decision making, or if the surrogate has a role in the patient's medication management. The following is assessed for each targeted medication: medication adherence, possible side effects, perceived benefit (or harm) of the medication, cost, and agreement/ disagreement to stopping or reducing the medication. As part of this interview the PharmD or NP may need to provide patient education about individual medications (e.g., side effects, risk-benefit, current evidence) and address any questions or concerns before asking if the patient agrees to deprescribe. If the patient raises a concern about a medication which the study team did not target for deprescribing, the PharmD or NP should still address these concerns and note them in communications with the treatment team. Finally, if a patient agrees to deprescribe a medication for which they have refills, the PharmD or NP informs them that we will be canceling the refills if their provider agrees.

Study clinicians take field notes during the interview in which they detail the patient's general comments about medications and prescribers as well as the rationale for the patient's agreement/disagreement with each deprescribing recommendation. After the interview these comments are coded into pre-set barriers and enablers (e.g., appropriateness, fear, process, influences, pragmatic, and dislike) from an established framework. Patient/surrogate comments can align with more than one category for each medication and should be coded as such. A second study team member, usually the study coordinator or data manager, independently reviews the interview comments and coded for agreement. If there is disagreement related to categorization, the team discuss the theme assignment until a consensus is reached.

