## Final Hospital Deprescribing Actions

The final in-hospital phase of the deprescribing protocol requires that the study PharmD or NP assimilate the data from all three phases (Figure 3. 2a, 2b, 2c) to finalize deprescribing actions. Deprescribing can begin at any time after randomization and following step 2a – 2c. All deprescribing actions are executed by the inpatient treatment team using recommendations from the study PharmD or NP. Recommendations include input from the intervention team, patient, inpatient treatment team, and the original prescriber(s) when available.

We anticipate that there will be disagreement between clinical reviewers, inpatient teams, primary prescribers and patients. The incidence and nature of the disagreement will be monitored closely. In anticipation of disagreement the following guidelines will be in place. First, deprescribing of pre-hospital medications will not be recommended to the treatment team (acute or post-acute) without patient agreement. Deprescribing of medications will be recommended against a patient's preferences when there is a clear indication of imminent safety threats as determined by the intervention pharmacist / NP, inpatient clinical team, or primary prescriber. Otherwise, we will first counsel the patient regarding the rationale for the deprescribing recommendation and seek consensus. If disagreement continues, we will monitor the medication throughout the intervention phase for side effects. In addition, we will highlight this medication at discharge for follow-up by the primary prescriber. All final deprescribing actions will be carried out by the inpatient treatment team.

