## PAC Handover and Ongoing Deprescribing at PAC Facility

Within 24-hours of transition to PAC, a study pharmacist or NP has a phone conversation with a designated PAC provider with prescribing authority (NP or physician) to review the Transfer Medication List, highlight deprescribed medications and the need for medication-specific monitoring. In addition, all medications recommended for deprescribing may not be stopped prior to hospital discharge in the interest of first monitoring symptoms and ensuring safety or due to delayed contact and input from the outpatient prescriber. Medications for additional deprescribing at the PAC may be highlighted during this initial handover and discussed again in weekly follow-up calls while the patient remains in PAC (Phase 3).

Following PAC handover, we initiate a weekly conversation via telephone with the designated PAC provider to review intervention participants' medication administration record (MAR) and any drug withdrawal events. Reasons for modifying the Transfer Medication List during the PAC stay will be discussed and intervened upon as necessary. The intervention also will continue for participants readmitted to VUMC directly from PAC (estimated 20%) and continue upon transfer back to the PAC. The study PharmD or NP may also continue to communicate with the original prescriber/ outpatient provider during the PAC stay to confirm their agreement with medication changes. At the time of discharge from the PAC facility, a final reconciled medication list will be sent to the patient's primary outpatient providers along with suggestions for continued medication management and deprescribing as well as any explanations for other medication changes made.

For analytical and feasibility purposes, the intervention ends at the point of discharge to home. If a patient discharges to home instead of a partner PAC facility, they will be withdrawn from the study and only considered to have one phase of the intervention. For safety reasons, the study team provides their outpatient provider with the final discharge medication list highlighting any symptom monitoring required.

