## STATISTICAL CONSIDERATIONS

### Sample Size and Randomization

Figure 1 illustrates the flow of participants through the study and estimated total sample sizes during each study phase based on prior data. The overall effectiveness of the intervention will be evaluated based on the primary outcome measure, which is total medication count. Based on current enrollment rate, we estimate that approximately 144 patients per year will enroll in the study, or 576 across all four years of enrollment. Among those, we estimate that 27.5% will either die or otherwise be lost from the study prior to the 90-day post PAC discharge follow up period. Thus, across all four years of enrollment, an estimated 420 patients will contribute measurements at 90 days. Although 567 is the expected total enrollment, we conservatively use 420 to estimate the statistical power associated with the assessment of overall effectiveness (i.e., overall completion rate) rather than enrollment rate, to account for estimated attrition across all study phases.

Preliminary data is available for the effect of deprescribing on the reduction in the counts of total medications. Our pilot intervention (N=40) was associated with roughly a 50% reduction in the count of total medications from enrollment to hospital discharge, whereas a roughly 25% reduction was observed in the control group receiving routine hospital care. Using these preliminary data and mixed-effects Poisson regression methods, we implemented a simulation-based power analysis wherein we assumed that this effect would be attenuated by 20% at SNF discharge, and again by 20% at the 90-day follow up. Using a sample size of 420, there is greater than 95% power to detect a 50% versus 25% reduction in total medications. There is approximately 90% power to detect a 30% versus 25% reduction in total medications, and 80% power to detect a 27.5% versus 25% reduction in total medications. Thus, the target sample size provides some protection against effects that are substantially smaller than that observed in our preliminary data.

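### The 90-day medication count is made by the same pharmacist/NP role that delivers the unblinded intervention, and nothing masks that assessor or keeps the treating clinician from counting

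*Combined protocol and SAP*

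**What the plan says.** The Sample Size and Randomization section says that overall effectiveness rests on the "primary outcome measure, which is total medication count". The Outcomes section models that count at hospital discharge, SNF discharge and 90 days after SNF discharge.

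Primary Outcomes - Medications describes the 90-day measurement. First, "In preparation for the 90-day visit, the study team completes a pharmacy record review similar to enrollment". Then "At the 90-day visit, the study PharmD or NP reviews all the medication bottles in the home". Whether a product counts as used is settled by self-report: the clinician "asks the patients if and how they are using each". The outcome includes prescription and OTC products, vitamins and herbal supplements. Table 1 counts routine and PRN drugs.

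The intervention sections give delivery to the same roles. Participants in the intervention arm "receive a structured interview by the intervention pharmacist (PharmD) or nurse practitioner (NP) to elicit their preferences". In Final Hospital Deprescribing Actions, "All deprescribing actions are executed by the inpatient treatment team using recommendations from the study PharmD or NP". In the PAC handover section, "a study pharmacist or NP has a phone conversation with a designated PAC provider with prescribing authority", followed by weekly calls.

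On follow-up staff in general, Study Procedures says: "All interview assessments are completed by trained research personnel on our multidisciplinary team". That team is described as including clinical pharmacists and geriatric nurse practitioners.

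**The concern.** At 90 days someone must decide whether a half-used bottle, an occasional PRN drug or a supplement counts as a current medication. In the intervention arm, that person may be the clinician who earlier persuaded the participant to stop it. No one stands in that position in the control arm. Two routes to differential recording follow. The assessor may resolve doubtful items differently by arm, and the participant may answer differently to the clinician with whom a stop was agreed.

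The PIM count, the count of drugs linked to geriatric syndromes and the Drug Burden Index appear to be built from the same medication data, so they would share any error. During COVID-19 the 90-day visit could be held by telephone or video, which may have made the count lean more on self-report.

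**Working it through.** **1. Roles side by side**

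| Task | Who does it | Section |
|---|---|---|
| Preference interview | intervention pharmacist or NP | Incorporate Patient Preferences |
| Prescriber contact | intervention or study pharmacist or NP | Outpatient Provider Input; Inpatient Provider Input |
| Final recommendations | study pharmacist or NP | Final Hospital Deprescribing Actions |
| Handover and weekly calls | study pharmacist or NP (handover); study team (weekly calls) | PAC Handover and Ongoing Deprescribing |
| 90-day count | study pharmacist or NP | Primary Outcomes - Medications |

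The adjectives study and intervention do not mark two separate groups: the recommendations and the 90-day count are assigned under the same label.

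**2. Where masking is stated.** It is stated for the physician adjudicators of utilization events and deaths (Safety and Healthcare Utilization Outcomes; Review of Unplanned Healthcare Utilizations and Deaths) and for initial DSMB reports (Meeting Processes and Outcomes). It is not stated for the medication assessor. The Limitations paragraph under Data Analyses plans a 7-day check of whether intervention participants still take stopped drugs, which implies that follow-up staff know the arm.

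**3. Room for judgement.** Primary Outcomes - Medications defines current use only for the 30 days before hospitalization. It gives no 90-day rule for bottles, PRN or OTC products, and does not say which source prevails when bottle, participant and pharmacy record disagree.

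**4. The plan's own sample size.** 576 × (1 − 0.275) = 417.6, against 420 stated, so the figure is reproduced. The concern does not change it.

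**5. A yardstick.** The smallest effect listed, at 80% power, is a 27.5% versus 25% reduction, or 2.5 points of the enrollment count. The trial's enrollment mean is not given, so I use a range:
- low: 14, the hospital-discharge mean in the preliminary cohort;
- high: about 25, inferred from the pilot (12.6 deprescribed / 0.50 = 25.2; the control arm gives 6.5 / 0.25 = 26).

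Then 0.025 × 14 = 0.35 drug per person, and 0.025 × 25.2 = 0.63. That equals one uncounted drug in every 1/0.35 = 2.9 to 1/0.63 = 1.6 intervention participants. If the plan's two 20% attenuations also apply to this scenario and compound (0.8 × 0.8 = 0.64), the 90-day figures fall to 0.22 and 0.40.

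This yardstick is soft because the stated powers do not fit one standard error. On the log-ratio scale, ln(0.75/0.725) = 0.0339 at 80% power needs SE = 0.0339/(1.960 + 0.842) = 0.0121. With that SE, 30% versus 25% (ln(0.75/0.70) = 0.0690) would have over 99.9% power, not about 90%.

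**6. Illustrative effect on error at 90 days.** Assumptions: no true effect; 210 per arm; control mean m_c = 0.75 × baseline; b drugs per intervention participant left uncounted, so m_t = m_c − b; SE = √[φ(1/(210 m_t) + 1/(210 m_c))], with dispersion φ; two-sided 5% Wald test. Example with baseline 14, b = 0.25, φ = 1: ln(10.5/10.25) = 0.0241, SE = 0.0303, ratio 0.80, rejection probability 12.5%.

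| b | φ = 1, baseline 14 to 25.2 | φ = 2, baseline 14 to 25.2 |
|---|---|---|
| 0.25 | 12.5% to 9.1% | 8.7% to 7.0% |
| 0.50 | 36.0% to 22.0% | 20.5% to 13.4% |

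The values of b are assumptions; the documents give no misrecording rate. The approximation ignores the baseline adjustment and the random intercept.

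**7. Against the pilot-size effect.** A 50% versus 25% reduction is 0.25 × 14 = 3.5 to 0.25 × 25.2 = 6.3 drugs. With both attenuations (0.25 × 0.64 = 0.16) it is 2.2 to 4.0. The yardstick of 2.5 points is 10% of the unattenuated effect and 16% of the attenuated one (0.025/0.16).

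**The case against.** The case for leaving the plan alone has real content.

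- **Safeguards exist.** Bottles are physically inspected, a pharmacy review precedes the visit, both arms have the same schedule and measures, interviews follow standardized protocols, and data are reviewed weekly. These reduce gross error. They do not equalize judgement about OTC, PRN and supplement use by someone who knows the arm.
- **90 days is one of three modelled time points.** The post-acute discharge outcome comes from the discharge list, not from a bottle review. This stands, so only part of the primary analysis is exposed.
- **Direction is open.** A reader might infer that the bias must favour the intervention. The documents do not show this. An assessor who knows which drugs were stopped may probe harder for restarts, as the 7-day check suggests, and that would raise the intervention count.
- **Same person.** A reader might infer that the treating clinician does count. The documents describe a shared role; they neither state nor exclude a shared individual.
- **Pharmacy records as a neutral check.** It is tempting to treat a pharmacy-record-only count as free of arm. It is not. The preference interview provides for cancelling refills once the prescriber agrees, and the Limitations paragraph plans contact with pharmacies as an intervention component. Both alter those records in the intervention arm. The study team does the review with no masking stated, and the records miss OTC products.

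**Conclusion.** The concern holds as a gap in the plan, not as demonstrated bias. An unmasked assessor, possibly the treating clinician, makes one of the three modelled measurements of the primary outcome without a written counting rule, and no other section closes the gap.

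Its size is unknown. Misrecording of about 0.35 drug per intervention participant (baseline 14) to 0.63 (baseline about 25) would match the smallest effect the plan says it can detect. Both baselines are assumptions, and the stated power behind that effect is itself hard to reconcile. A reader might go further and infer that assessor bias could manufacture a positive trial. If the true effect is near the pilot's, bias of this size could not account for it. The gap matters if the observed difference is small.

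**What to change.** In Primary Outcomes - Medications:

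1. Assign each 90-day visit to a team pharmacist or NP who did not deliver that participant's intervention and, where feasible, is not told the arm. This is the step that matters most.
2. Write one counting rule for bottles, PRN drugs, OTC products and supplements, including which source prevails in a conflict, and apply it identically in both arms.
3. Have the final count coded from the recorded list by a team member masked to arm. This is a modest addition, because it cannot undo biased recording at the visit.

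For visits already done, record who made each count and whether that person treated the participant, and report the limitation. Masked coding from the retained paper forms is still possible.

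A pharmacy-record-only count may be shown as a supplementary description, with the refill, pharmacy-contact and OTC caveats stated, but not as an arm-neutral sensitivity analysis.

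The cost is less flexible scheduling, a short written rule and some coding time. Staff headcount is not given, but Study Procedures and Outpatient Provider Input refer to pharmacists and NPs in the plural, so reassigning visits within the existing team looks feasible. Sample size and the primary model are unchanged.

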## **Secondary Outcomes - Geriatric Syndromes, Medication Adherence, Functional Health Status**

**Delirium:** The Brief Confusion Assessment Method (bCAM) is a brief screening tool for delirium and has been validated among hospitalized, older patients. If the participant screens positive for delirium, no other participant interviews are conducted at that time. Research personnel continue to re-assess delirium daily during hospitalization; and, when the participant screens negative for delirium via the bCAM, the remaining assessments are administered to the participant. If delirium continues throughout the hospital stay or the participant is otherwise unable or unwilling to complete the assessments, the surrogate is approached for a subset of the geriatric syndrome assessments (i.e., incontinence, nutrition and fall history). The bCAM is not repeated by research personnel at 7-day follow-up because it has limited validity when administered via the telephone; thus, it is repeated only at 90-day follow-up during the in-person home visit. Additionally, PAC personnel use the CAM (i.e., the Confusion Assessment Method, [CAM]), which is a modified version of the bCAM, to assess delirium during the PAC stay via the MDS assessment.

**Cognitive Impairment:** The Brief Interview for Mental Status (BIMS) is a short, validated assessment of cognitive impairment with a total score range from 0 to 15 (0-7: severe impairment; 8-12: moderate impairment; 13-15: cognitively intact). The BIMS is routinely used in the SNF care setting as part of required MDS assessments for all SNF patients upon admission and discharge and following a hospitalization event.

**Depression:** The Patient Health Questionnaire (PHQ) is a validated tool to assess depression symptoms and severity. Each item is scored from 0 (“not at all”) to 3 (“nearly every day”) to yield a total score range from 0 (no depressive symptoms) to 27 (severe depression). In the event that a participant reports severe depression or thoughts of self-harm, the study team elicits more information to evaluate their immediate safety then contacts the primary treatment team to address this with the participant. The PHQ-9 is routinely used in the SNF care setting as part of required MDS assessments.

**Urinary Incontinence:** The International Consultation on Incontinence Questionnaire - Urinary Incontinence Short Form (ICIQ-UI SF) consists of four items that assess the symptoms, frequency and impact of urinary incontinence on quality of life. This tool has well established reliability (Cronbach’s alpha = .95) and validity, including sensitivity to treatment. The MDS has one item for incontinence frequency scored 0 ‘always continent’ to 3 ‘always incontinent’.

**Unintentional Weight Loss and Poor Appetite:** We use the same structured interview used in our prior study to assess recent changes in weight and/or appetite in addition to the 10-item “Determine Your Nutritional Health checklist”, which yields a total nutritional risk score of: 0-2 (“low”), 3-5 (“moderate”), or  $\geq 6$  (“high”). The DETERMINE checklist has been validated in a longitudinal study of community-dwelling older adults. If the participant endorses a weight change of 10 pounds or more on the DETERMINE item, a structured follow-up question is posed to clarify whether the weight change reflects a gain versus a loss. The MDS has one item for unintentional weight loss, defined as 5% or more in 30 days or 10% or more in 180 days.

**Pain:** Pain will be assessed using the Brief Pain Inventory (BPI) Short-Form, which is a validated instrument for assessing pain location, severity, and interference with daily activities among older adults. Pain severity is based on four questions wherein participants use a 0 (no pain) to 10 (worse pain imaginable) scale to rate their pain in the last 24-hours under four conditions: at its worst, at its least, on average, and now. Pain is assessed in the PAC setting via the MDS, which includes items related to pain frequency, effect on function and intensity.

**Falls:** The patient/surrogate is asked if the patient has fallen in the last month or since the previous timepoint during the follow-up phase. If the response is ‘yes,’ then the patient is asked how many times they have fallen, and that number is recorded. Finally, the study team asks if any of the falls led to either an emergency room visit or hospitalization.

Pressure Ulcers: The presence of pressure ulcers (Stages 0 – 4) will be abstracted from the hospital medical record (flowsheets) at baseline and confirmed via direct interview with the patient and/or family. Similarly, this same information will be, again, abstracted from the PAC medical record and confirmed via patient/family interview during an in-person visit 7 and 90-days post PAC discharge.

Adherence to Refills and Medications Scale (ARMS): The ARMS consists of 12 items to assess overall medication adherence, with a total score range of 12 to 48. A lower score is indicative of better medication adherence. Example questions include: “How often do you forget to take your medicines?”, “How often do you miss taking your medicines when you feel better?”, and “How often do you put off refilling your medicines because they cost too much money?” Response options are on a 4-point Likert scale that ranges from “none of the time” to “all of the time.”

Vulnerable Elders Survey (VES-13) is a functional measure of health status that assesses a patient’s cognitive, physical and self-care activities and which also includes an item for self-rated health status. Scores range from 1 to 10, with lower scores indicative of better health.

